3.2.3 TERTIARY

OBJECTIVES	ENDPOINTS	JUSTIFICATION FOR ENDPOINTS
Tertiary/Exploratory		

 Among the vaccinated group only, to compare Primary Endpoint and Secondary Endpoints 1-7 between high responders and low responders, defined by RVNA titers measured by rapid fluorescent foci inhibition test (RFFIT) at day 180 after first vaccination. Explore latency period and duration of effect on Primary Endpoint and Secondary Endpoints 1-5. Explore the effect of dose (1 vs. 2 vs. 3) on Primary 	
 Primary Endpoint and Secondary Endpoints 1-7 Primary Endpoint and Secondary Endpoints 1-5 Primary Endpoint and Secondary Endpoints 1-5 	See above

OBJECTIVES	ENDPOINTS	JUSTIFICATION FOR ENDPOINTS
Endpoint and Secondary Endpoints 1-5.		

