6.3 DOSING AND ADMINISTRATION

Dosing and administration of the vaccine (Rabivax-S) will be according to the package insert, following the schedule for pre-exposure prophylaxis via the intramuscular route; that is, 1 mL by intramuscular injection in the deltoid area of the arm on Day 0, Day 7 and Day 21. Dosage and administration of the placebo (sterile water for injection) will follow the same schedule and route of administration; that is, 1 mL by intramuscular injection in the deltoid area of the arm on Day 0, Day 7 and Day 21. In the event of interruption of the schedule of administration (of either the vaccine or the placebo), the schedule will be

resumed without repeating a previous dose (as per Table 3 Recommendations for Interrupted or Delayed Routine Immunization – Summary of WHO Position Papers, updated April 2018; http://www.who.int/immunization/policy/immunization_tables/en/).

Vaccine and placebo will be administered to participants at the RUSVM Student Health Services by study nurses or nurse practitioner, using a 25G (0.50 x 25mm) needle and 2 mL syringe.

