6.4 STUDY INTERVENTION COMPLIANCE

The number of doses received, and the date received, will be recorded by study personnel at RUSVM Student Health Services in Case Report Forms (CRF) for Visits 1-3. An entry will also be made in students' health records at RUSVM Student Health Services.

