6.5 DISCONTINUATION OF STUDY INTERVENTION

Prior to administration of each dose of either the vaccine or placebo, participants will be assessed by personnel at the RUSVM Student Health Services for contraindications to the vaccine (see **Section 5.2.3, Screen Failures** for listed contraindications). Individuals with a contraindication requiring postponement of vaccination may return once the condition is resolved to resume the intervention for their allocated group (vaccine or placebo), so long as this occurs before study completion (see **Section 7, Participant Timeline** for definition of study completion). In the event of interruption of the schedule of administration (of

either the intervention or the control), the schedule will be resumed without repeating a previous dose (see **Section 6.3, Dosing and Administration** for details).

Participants for whom the study intervention was halted, due to absolute contraindications or other clinically-relevant event, or for whom intervention was postponed beyond the time of study completion, will remain in the study and complete the weekly illness surveys.

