7 PARTICIPANT TIMELINE

Students will be informed about the trial prior to the start of the semester for which they are eligible (orientation week for VP and 1st semester cohorts, and at the end of 4th semester for 5th semester cohorts). Students will be recruited into the study during orientation week and/or the first week of the semester, and will receive the first injection (day 0) within the first two weeks of the semester. Participants will receive the second injection on day 7 and the third injection on day 21. If necessary, participants can begin the intervention later, so long as day 0 falls within the first 12 weeks of the semester (see **Section 5.2.2, Exclusion criteria** for details).

Weekly illness surveys will begin in study week 3 (Monday of study week 3, day 10-14 after first injection) for all participants, and will continue for 26 weeks (through week 11 of the following semester in the case of a two-week semester break, or week 10 of the following semester in the case of a three-week semester break). One week after receipt of the final (26th) weekly survey, participants will be unmasked and will exit the study. Following exit, participants who were allocated to the control group will begin a primary course of rabies

vaccine in weeks 11 or 12 (depending on 3- or 2-week semester break), to be completed by the end of the semester (weeks 14 or 15).

A participant is considered to have completed the study one week after receipt of the final (26th) weekly survey.

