12 DATA COLLECTION METHODS

After enrollment, participants will complete a questionnaire that will capture data on relevant baseline characteristics including sex, age, health and vaccination status. (Baseline CRF; Appendix C). Participants will complete a short survey each week, starting in study week 3, to capture self-reported episodes of illness (respiratory, diarrheal and febrile illness; Primary Endpoint and Secondary Endpoints 1-5) in the preceding week (Appendix G). Surveys will be sent by email to all participants each Monday. Participants who have not completed the survey by Wednesday afternoon will be sent a request by email to complete the survey for the preceding week. Surveys will be sent weekly, for 26 weeks. A participant is considered to have completed the study one week after receipt of the final (26th) weekly survey for that participant's cohort.

As an incentive to enhance participant retention and response rates in weekly illness surveys, all participants who complete a weekly survey will be entered into a draw each week for a chance to win a EC\$25 gift voucher to a food/beverage vendor on the RUSVM campus. Selection of a winner each week will be done by computer-generated random sampling. The weekly winner will be notified by email in the week following the draw.

Clinically- and laboratory-confirmed episodes of study syndromes (Secondary Endpoints 6 & 7) will be collected by study personnel at RUSVM Student Health Services, as part of the

routine clinic visits and diagnostics. At the end of each 26-week observation period for each study cohort, data from that cohort will be compiled by the director of the RUSVM Student Health Services, anonymized to protect privacy and aggregated by study arm, before being sent to the Data Analyst who will conduct the analysis.

Occurrence of expected Adverse Events (Safety Endpoint 1) will be solicited in an online survey (Appendix H) sent to participants 3 days after receiving an injection (for dose 1, 2 and 3). Occurrence of unsolicited adverse events and serious adverse events (Safety Endpoint 2) will be captured by study personnel at RUSVM Student Health Services through completion of an Adverse Event form (Appendix I; See **Section 15.3, Identification of Adverse Events** for details).

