Participants in the vaccine efficacy ancillary study will have a maximum volume of 8 mL of blood collected by venipuncture prior to injection on day -7 (acceptable range -3 through -11), and again on day 180 (acceptable range 173 through 187). Serum will be separated and stored at -20 °C at RUSVM until transport to the laboratory for measurement of RVNA by RFFIT. Serum specimens will be labelled with participant study identification numbers only. No other participant information will be sent to the laboratory.

Participants in the immunology ancillary study will have a maximum volume of 10 mL of blood collected by venipuncture prior to injection on day 0, and again on days 21 and 90. Blood specimens will be immediately taken to the RUSVM Research Laboratory for

isolation of PBMCs. Blood specimens will be labelled with participant study identification numbers only. No other participant information will be sent to the laboratory.

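### The exploratory high/low antibody-responder comparison takes no account of dose number or dose timing, and its titer is drawn after most of the outcome is collected (minor)

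*Combined protocol and SAP*

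**What the plan says.** Section 3.2.3, headed tertiary/exploratory, compares the primary endpoint and secondary endpoints 1-7 between high and low responders within the vaccinated group, "defined by RVNA titers measured by rapid fluorescent foci inhibition test (RFFIT) at day 180 after first vaccination". No cut-off between high and low is given. Section 14 promises further detail in a SAP for the primary and secondary endpoints and does not mention this analysis.

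The surrounding timing is as follows.

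- **Doses.** Section 7: "Participants will receive the second injection on day 7 and the third injection on day 21". Under Section 6.3 an interrupted course is "resumed without repeating a previous dose". Section 6.5 lets a postponed dose be given "so long as this occurs before study completion", and Section 7 puts completion one week after the 26th survey.
- **Reasons for postponement.** Section 5.2.3 lists fever or acute illness among them, and Section 6.5 applies that list before every dose.
- **Draw.** Section 12 sets the second blood sample: "again on day 180 (acceptable range 173 through 187" (days, counted from the first injection).
- **Outcome.** Section 7: "Weekly illness surveys will begin in study week 3 (Monday of study week 3, day 10-14 after first injection) for all participants". Section 12: "Surveys will be sent weekly, for 26 weeks".
- **Who has titers.** Section 3.2.5 plans them in three 2019 cohorts, about 350 participants over both arms.
- **What is recorded.** Section 6.4: "The number of doses received, and the date received, will be recorded".

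**The concern.** The label is meant to capture how strongly a person responded to the vaccine. A titer timed from the first dose also depends on how many doses preceded the draw and how long ago the last one was. If titers fall with time and rise after a dose, which the retest-and-booster advice cited in Section 5.1 implies, a late last dose pushes a person towards the high group for reasons unrelated to responsiveness. An incomplete course can push the other way.

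The timing problem can also connect to the outcome. An illness at the time of dose 2 or 3 postpones that dose, brings it closer to the draw and so may raise the day-180 titer. Illness around day 21 falls within the surveyed period, so it can also count as an endpoint episode. That would make high responders look sicker.

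Separately, the grouping variable is measured when the outcome is almost fully collected, and only in those still available at about day 180.

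At stake is the plan's one comparison linking rabies antibody to illness rates. A difference, or its absence, could be misread as evidence about mechanism.

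**Working it through.** **1. The plan's own figure, to check the variance formula used in step 6.** Inputs from Section 8: control rate 2, rate ratio 0.75 (so 1.5 under vaccine), participation 0.8, dispersion 0.4, two-sided alpha 0.05, power 0.8.

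n per arm = (1.960 + 0.842)² × [(1/0.8)(1/2 + 1/1.5) + 2 × 0.4] / (ln 0.75)² = 214.2, rounded up to 215, or 430 in total. This matches Section 8. The present point does not depend on it.

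**2. Surveys sent before the draw.** Survey j goes out on day s + 7(j − 1), with s from 10 to 14. Survey 26 is therefore sent on days 185-189, and completion falls on days 192-196. The number sent by day d is floor((d − s)/7) + 1.

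| Draw day | s = 10 | s = 14 |
|---|---|---|
| 173 | 24 | 23 |
| 180 | 25 | 24 |
| 187 | 26 | 25 |

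At day 180 that is 24-25 of 26 (92-96%). Over the allowed window it is 23-26 (88-100%).

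**3. Days from last dose to draw.**

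- Three doses on schedule: 180 − 21 = 159; over the window, 173 − 21 = 152 to 187 − 21 = 166.
- Doses 1 and 2 only: 180 − 7 = 173.
- Dose 1 only: 180.
- Postponed dose: anything shorter, down to zero. It may even follow the draw, because dosing may resume until about day 192-196.

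**4. Information lost by splitting.** If the cut were at the median of a normally distributed log titer, the split keeps 2/π = 0.637 of the information, a loss of about 36%. Vaccinees with titers: 350/2 = 175 under 1:1 allocation. 175 × 0.637 ≈ 111.

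**5. Illustration of mislabelling.** The documents give neither the late-dose share nor the waning rate, so this rests on assumptions: log10 titer SD 0.3 or 0.5; titer half-life 60 or 120 days; a last dose 14-159 days late (uniform) in 5% or 30% of vaccinees; median cut; 400,000 simulated participants.

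| SD, half-life | Late share | Labelled high: late / on schedule | Labels changed | Late share of high / low group |
|---|---|---|---|---|
| 0.3, 60 | 5% | 87% / 48% | 3.7% | 8.7% / 1.3% |
| 0.3, 60 | 30% | 81% / 37% | 18.8% | 48.8% / 11.2% |
| 0.5, 120 | 5% | 66% / 49% | 1.6% | 6.6% / 3.4% |
| 0.5, 120 | 30% | 62% / 45% | 7.1% | 37.2% / 23.0% |

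The other two combinations (0.3 with 120, 0.5 with 60) lie between these at each late share.

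**6. What that could do to the illness comparison.** Assume further that late-dose participants have twice the illness rate. The spurious high/low rate ratio is (1 + late share of high group)/(1 + late share of low group).

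- 5% late: 1.066/1.034 = 1.03 to 1.087/1.013 = 1.07.
- 30% late: 1.372/1.230 = 1.12 to 1.488/1.112 = 1.34.

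For comparison, take about 87 per group and the Section 8 inputs (rate 1.5, participation 0.8, dispersion 0.4). The standard error of the log rate ratio is √[(2/87)(1/(0.8 × 1.5) + 0.4)] = 0.168. The 95% interval then reaches a factor of exp(1.96 × 0.168) = 1.39 either way.

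**The case against.** The analysis is exploratory and feeds no sample size, decision rule or primary conclusion. Everyone on schedule is drawn at 159 days, give or take 7, so the timing problem needs late or missed doses. The documents do not say how many there will be, and fever or acute illness is usually brief. Section 5.2.3 also requires, when a person is rescreened before the first dose, that the course can still finish before the semester break. Even with a doubled illness rate, the spurious ratio in step 6 is smaller than the sampling error.

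Most of this stands and sets the severity. It does not remove the point. The semester-break condition governs rescreening before allocation, while Section 6.5 sets the looser limit for later doses. The order of titer and outcome affects everyone, on schedule or not.

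Four stronger readings are not supported:

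- **Recency generally drives the label.** It can act only through off-schedule or incomplete courses.
- **The percentages in step 5 are estimates for this trial.** They follow from assumed inputs. They are also label shares, not bias in the rate ratio; bias needs a further link such as illness postponing a dose.
- **The plan specifies a median split.** It states no cut-off, so the 36% loss is conditional.
- **At most about 150 vaccinees will have titers.** This might be inferred from the expected enrollment below 100 per semester in Section 8. Section 3.2.5 states about 350 for this sample, hence about 175 vaccinees. The proportional loss is the same on either basis.

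**Conclusion.** The concern holds as a minor point about an exploratory analysis. The high/low label mixes response with dose number and dose timing for vaccinees whose course was incomplete or postponed, and early illness could feed into it. The size of that effect cannot be computed from the documents. Under the assumptions in step 5, it ranges from about 2-4% of labels changed (5% late) to 7-19% (30% late).

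Two parts do not depend on late doses. With 24-25 of 26 surveys sent by day 180, the titer cannot be read as predicting illness. Splitting a continuous titer also loses information, about 36% if the cut is at the median of a normal log titer. The primary conclusion is untouched.

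**What to change.** In Section 3.2.3, make the main analysis log2 RVNA titer as a continuous term in the negative binomial model, among vaccinated ancillary-study participants with a day-180 titer. Adjust for the number of doses received before the draw and for days from last dose to draw. Keep any high/low grouping as a descriptive display. State that the result is an association with a titer measured after most of the outcome period.

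Add a sensitivity analysis in participants who received all three doses on or near schedule, with near schedule defined in advance. Do not use a fixed minimum such as 150 days: a participant drawn on day 173 with dose 3 on day 24 has an interval of 149 days and would be dropped for a three-day delay. Restricting by timing can also select on early illness, which is why it should not be the main analysis. Requiring an undetectable day -7 titer is unnecessary here, since Section 5.2.2 already excludes anyone with a previous dose.

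The cost is wording only, because dose dates and the day-180 titers are already collected. The price is a log-linearity assumption and a more modest claim. The order of titer and outcome is acknowledged, not repaired.

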3.2.4 SAFETY

OBJECTIVES	ENDPOINTS	JUSTIFICATION FOR ENDPOINTS
Safety		

 • To compare, between the same two groups, 
 1) The rate of solicited adverse events (AEs) through 3 days after each injection (dose 1, 2 and 3) 2) The rate of unsolicited adverse events and serious adverse events (SAEs) through four weeks after first injection • As a secondary objective, sub-group analysis for potential effect measure modification of safety endpoints by sex (males or females) 	
 1. Number of solicited self-reported events over three days following each injection of the following adverse events: 
 a. Local reactions (limited to the site of the injection): pain, erythema, oedema, pruritus and induration. b. Systemic reactions: fever, shivering, malaise, asthenia, faintness, dizziness, headache, myalgia, arthralgia, nausea and abdominal pain. c. Hypersensitivity or allergic reactions: anaphylaxis, urticaria, rash and erythema multiforme. 2. Number of unsolicited adverse events and SAEs reported to RUSVM Student Health Services through four weeks after first injection 	
Solicited adverse events are those adverse events listed in the package insert of the study intervention (Rabivax-S rabies vaccine)

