14 STATISTICAL METHODS

The analysis of the primary endpoint and secondary endpoints 1-7 will be conducted after all randomized participants have completed the study (one week after receipt of the final weekly survey) or have withdrawn from the study, whichever occurs first. Primary analysis will be based on intention-to-treat analysis of all events (that is, not just occurrence of first events). The comparison of incidence rates of CID episodes (primary endpoint and secondary endpoints 1-7) between the treatment arms will be performed using a negative binomial regression model, which accounts for different lengths of observation period. Participants' number of CID episodes will be modelled as a function of treatment group, with the number of weeks of observation included as an offset in the model. This analytic model estimates the rate ratio, λ_t / λ_c , which quantifies the risk of CID episodes associated with rabies vaccination (λ_t) in comparison to placebo injection (λ_c). Statistical significance will be controlled at the 2-sided, 0.05 alpha level, and the estimated rate ratio compared with 1, assuming the following statistical hypothesis:

H_0 (null hypothesis): Rate ratio = 1

H_1 (alternative hypothesis) Rate ratio $\neq 1$

Treatment effect will be based on the coefficient in the model. Statistical significance at the pre-specified alpha level will be based on a Wald testing procedure. CID rates (primary

endpoint and secondary endpoints 1-7) for rabies vaccine and placebo, and the rate ratio, will be presented and will include 95% confidence intervals.

A detailed description of the statistical methods that will be used for the primary and secondary endpoints will be provided in a Statistical Analysis Plan (SAP).

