15.2 CLASSIFICATION OF ADVERSE EVENTS

All adverse events (AEs) will have their relationship to study intervention assessed by the Manager of the RUSVM Student Health Services (study nurse practitioner), in consultation with the study Medical Advisor, based on temporal relationship and clinical judgment.

The following guidelines will be used to describe severity:

- **Mild** – Events require minimal or no treatment and do not interfere with the participant's daily activities.
- **Moderate** – Events result in a low level of inconvenience or concern with the therapeutic measures. Moderate events may cause some interference with functioning.
- **Severe** – Events interrupt a participant's usual daily activity and may require systemic drug therapy or other treatment. Severe events are usually potentially life-

threatening or incapacitating. Of note, the term “severe” does not necessarily equate to “serious”.

The degree of certainty about causality will be graded using the categories below.

- **Related** – The AE is known to occur with the study intervention, there is a reasonable possibility that the study intervention caused the AE, or there is a temporal relationship between the study intervention and event. Reasonable possibility means that there is evidence to suggest a causal relationship between the study intervention and the AE.
- **Not Related** – There is not a reasonable possibility that the administration of the study intervention caused the event, there is no temporal relationship between the study intervention and event onset, or an alternate etiology has been established.

Adverse events will also be classified as **expected** or **unexpected**. An AE will be considered unexpected if the nature, severity, or frequency of the event is not consistent with the risk information previously described for the study intervention. Based on the information contained in the package insert for Rabivax-S, the following adverse events are considered expected:

- Local reactions (limited to the site of the injection): pain, erythema, oedema, pruritus and induration.
- Systemic reactions: fever, shivering, malaise, asthenia, faintness, dizziness, headache, myalgia, arthralgia, nausea and abdominal pain.

- Hypersensitivity or allergic reactions: anaphylaxis, urticaria, rash and erythema multiforme.

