15.3 IDENTIFICATION OF ADVERSE EVENTS

The Study Coordinator will review the Visit 1-3 CRFs daily for participants receiving injections (dose 1, 2 or 3). The study coordinator will send a link to an online Qualtrics survey (Appendix H) by email on day 3 after the date of the injection (dose 1, 2 or 3) to all participants. Information on occurrence of expected AEs will be specifically solicited in the survey, by asking the question, “Since receiving the study injection 3 days ago, did you experience any of the following...?” and providing participants with a list of expected AEs (see **Section 15.2, Classification of adverse events** for details) from which to select. Participants will also be asked to grade the severity of any AEs (mild, moderate or severe) and the outcome (recovered/resolved without sequelae, recovered/resolved with sequelae or ongoing). Information on occurrence of other AEs (unsolicited) will be sought by asking the question, “Besides the signs listed above, have you noticed anything different since starting the study?”, and providing participants the opportunity to describe what they noticed or experienced, and grade the severity and outcome as above.

Participants will also be encouraged to report any adverse events to RUSVM Student Health Services (unsolicited adverse events). An adverse event form (Appendix I) will be completed for all adverse events reported to RUSVM Student Health Services, using the Vaccine Adverse Event Reporting System (VAERS) writable PDF form (https://vaers.hhs.gov/pdf/vaers_form.pdf). The Principal Investigator, together with the

Director of the RUSVM Student Health Services, will review and compare the reports of unsolicited adverse events (adverse event forms) against reports of solicited adverse events in the AE surveys, to avoid double capture.

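### Safety Endpoint 1 compares solicited reactions between arms only as an ungraded count, so a shift in the severity of non-serious reactions at a similar count would not show in any stated arm comparison

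*Combined protocol and SAP*

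**What the plan says.** Section 3.2.4 sets two between-arm safety comparisons. The first concerns solicited events in the three days after each injection, and its endpoint is "Number of solicited self-reported events over three days following each injection of the following adverse events" (local, systemic and hypersensitivity reactions). The second is "Number of unsolicited adverse events and SAEs reported to RUSVM Student Health Services through four weeks after first injection". Neither mentions severity grade, and the only further safety analysis named is effect modification by sex.

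Grade is nevertheless collected. Section 15.3 says of the day-3 survey: "Participants will also be asked to grade the severity of any AEs (mild, moderate or severe) and the outcome". Section 15.2 defines the grades. On moderate events it says "Moderate events may cause some interference with functioning". It describes severe events as interrupting "usual daily activity and may require systemic drug therapy or other treatment. Severe events are usually potentially" life-threatening or incapacitating, and adds that severe need not mean serious.

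Section 14 gives the model for the primary endpoint and secondary endpoints 1–7. It then says "A detailed description of the statistical methods that will be used for the primary and secondary endpoints will be provided in" a SAP. It does not name the safety endpoints.

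**The concern.** A count gives a mild sore arm and a reaction that keeps a student in bed the same weight. If the vaccine changes how bad reactions are more than how many there are, Endpoint 1 does not register it. The arms are randomised and participants are blinded, so the self-grades allow a fair comparison of tolerability, which the plan as written does not use. Naming the grade cuts in advance also prevents their being chosen after the data are seen. What is at stake is the tolerability description. The efficacy conclusion is not involved.

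**Working it through.** **1. The plan's own figure.** The only sample size calculation is for the primary endpoint (Section 8). For two negative binomial rates with true-rate variance,

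n per arm = (z₀.₉₇₅ + z₀.₈₀)² × [(1/t)(1/r₀ + 1/r₁) + 2k] / (ln RR)²

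With r₀ = 2, RR = 0.75, r₁ = 1.5, t = 0.8 and k = 0.4:

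7.849 × [1.25 × (0.5 + 0.6667) + 0.8] / 0.08276 = 7.849 × 2.2583 / 0.08276 = 214.18, rounded up to 215 per arm, or 430 in total.

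This reproduces the stated size. The safety point does not depend on it; 215 per arm is used below only to gauge precision.

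**2. Where grade is collected and where it is used.**

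| Section | Grade collected or defined? | Used to compare arms? |
|---|---|---|
| 3.2.4, Endpoint 1 | no | compared as a count |
| 3.2.4, Endpoint 2 | no (seriousness only) | compared as a count |
| 14 | no | safety endpoints not covered |
| 15.2 | defined; severity also bears on expectedness | no |
| 15.3 | self-graded per event | no |
| 15.4 | related unexpected events and all SAEs to the IRB | no, case by case |

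**3. Simple illustration.** The documents give no reaction rates, so every rate here is assumed. Let the same fraction R of participants react in each arm. The expected difference in an ungraded comparison is then zero, and a two-sided 5% test rejects about 5% of the time whatever the severity mix. This holds by construction. For the graded comparison, p = R × (moderate-or-severe share of reactors). The 95% half-width is 1.96 × √{[p₀(1−p₀) + p₁(1−p₁)]/215}, and power is that of the pooled two-proportion test.

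| R | share, placebo vs vaccine | p₀ vs p₁ | difference ± half-width (points) | power |
|---|---|---|---|---|
| 30% | 10% vs 20% | 3% vs 6% | 3 ± 3.9 | 32% |
| 50% | 10% vs 20% | 5% vs 10% | 5 ± 5.0 | 50% |
| 70% | 10% vs 20% | 7% vs 14% | 7 ± 5.8 | 66% |
| 30% | 10% vs 30% | 3% vs 9% | 6 ± 4.5 | 75% |
| 50% | 10% vs 30% | 5% vs 15% | 10 ± 5.6 | 94% |
| 70% | 10% vs 30% | 7% vs 21% | 14 ± 6.4 | 99% |

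For R = 50% and shares of 10% vs 30%: 1.96 × √[(0.0475 + 0.1275)/215] = 0.056.

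**4. Repeated events per person.** A simulation allows for clustering. It assumes gamma-Poisson counts over all doses with mean 2 (or 4) and dispersion 1, equal counts in the arms, and a within-person severity correlation of 0.2–0.4. Power of a maximum-grade comparison at 215 per arm, with shares now taken over events:

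- Severe, 1% vs 2%: 14–16% (mean 4: 20–25%).
- Severe, 2% vs 6%: 64–70% (80–90%).
- Moderate-or-severe, 15% vs 25%: 66–67% (80–81%).
- Half-widths across the scenarios: 2.5–5.4 points for severe and 7.4–9.3 points for moderate-or-severe.

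If only 80% return surveys (172 per arm, assumed), severe 2% vs 6% falls to 54–61% (72–82%). For a single dose carrying a third of the events (assumed), severe 2% vs 6% has 31–34% (52–58%).

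The count does work for what it measures. Under the same model a 1.5-fold rise in events is detected with 94% (97%) power, and a 1.25-fold rise with 49% (55%).

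**The case against.** **Severity already has a formal use.** Section 15.2 lets severity make an event unexpected, and Section 15.4 sends related, non-serious unexpected events to the IRB within 48 hours. This stands. A reader might infer that a severe non-serious reaction would pass unnoticed, and the documents do not support that. Case reporting does not compare arms, however, so a modest shift in the mix could still be missed.

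**Serious events and clinic reports are covered.** SAEs are in Endpoint 2, and Section 15.3 adds "Participants will also be encouraged to report any adverse events to RUSVM Student Health Services (unsolicited adverse events"). Section 12 confirms the route: "Occurrence of unsolicited adverse events and serious adverse events (Safety Endpoint 2) will be captured by study personnel at RUSVM Student Health Services". A reader might infer that a solicited reaction also reported to the clinic ends up in Endpoint 2. The text does not establish this, because Section 15.3 reconciles clinic and survey reports to avoid double capture and does not say which count keeps the event.

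**An endpoint definition is not a table list.** Grades are collected and are meant to describe severity, so they may well be reported. This stands in part: silence does not show that grades would be dropped, and a later SAP could add them. But its stated scope is the primary and secondary endpoints, and the arm comparison that is stated is ungraded.

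**Self-grades are not clinical grades.** The text reviewed does not show whether participants see the Section 15.2 definitions; the survey form is an appendix that was not available. The figures above assume no misgrading.

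**No evidence of such a shift.** Nothing in the documents suggests equal counts with worse reactions, and the vaccine is already in routine use at the site. This stands, and it keeps the priority low.

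**Conclusion.** The point holds in a limited form. Grade is collected for each solicited event, yet no stated between-arm comparison uses it. A change in non-serious severity at a similar event count would therefore not appear in the planned comparisons. Individual severe cases and SAEs retain their own routes, so only the aggregate comparison is missing.

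That the count cannot see severity when counts are equal does not depend on any assumed rate. How much a graded table would add does. On the assumed rates, a clear shift in moderate-or-severe reactions could be estimated usefully. A rare severe reaction (1% vs 2% of events) could not, with power of 14–25% at 215 per arm. A reader might infer that the trial would then have an adequate test for severe reactions; it would not, and the addition should be presented as estimation. The primary test, sample size and alpha are unaffected. This is a cheap improvement of low priority.

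**What to change.** Keep the event count in Section 3.2.4 and add to Endpoint 1 the number and proportion of participants per arm whose maximum self-graded severity is (a) moderate or severe and (b) severe.

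- Give risk differences with 95% intervals for two comparisons only: after dose 1, and over all doses.
- Over all doses, take as denominator the participants with at least one completed adverse event survey, and report the number of surveys per participant by arm. After dose 1, the relevant survey is the dose-1 survey.
- Present grade tables for dose 2, for dose 3, by reaction class and by term as descriptive. Note that Section 6.5 allows injections to be halted or postponed, so participants with bad dose-1 reactions may not receive later doses.
- State that these are estimates without multiplicity-controlled testing. There are 2 grade cuts × 2 comparisons = 4 intervals. With no true difference, the chance that at least one excludes zero is 1 − 0.95⁴ = 19% if they were independent; they overlap heavily, so it should be lower.

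The cost is a few sentences of protocol or SAP wording and one extra table from data already collected. The downside is imprecision for rare severe reactions.
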